6.1.1 Recommendations for Use of Optune

All patients will be required to shave their heads to initiate array placement and Optune therapy. Array placement will be performed based on the transducer array map calculated during treatment planning. Optune is programmed by Novocure to deliver 200 kHz TTFields in two sequential, perpendicular field directions at a maximal intensity of 707mARMS. There will be no adjustments made to the device by investigators or patients/caregivers.

It is recommended that patients replace the transducer arrays 2-3 times per week with the help of a caregiver. At each array replacement, it is recommended that the patient's scalp be reshaved and skin treated according to the guidelines in section 6.1.2.

There will be no dose adjustments to the device for adverse events.

6.1.2 Skin Care Guidelines

If the skin beneath the transducer arrays is inflamed, it is recommended that a prescription strength steroid ointment (e.g. 3% hydrocortisone or 0.05-0.1% Clobetasol) be prescribed to the patient. The patient or caregiver should apply the ointment after removing the arrays and cleaning the scalp with baby oil and gentle soap. The ointment should be left on the scalp for

at least 30 minutes prior to washing the skin with a mild shampoo and applying a new set of arrays.

At each array replacement, it is recommended that the new set of arrays be shifted by approximately 2 cm compared to the previous layout so that the array discs are placed between the areas of skin irritation. At the next array replacement, the arrays should be shifted back to their original location.

If the dermis is breached (ulcers, open sores, punctate lesions, cuts, etc.), it is recommended that an antibiotic ointment (e.g. bactroban) be prescribed and used in place of the steroid ointment.

6.1.3 Potential Adverse Events: Optune

Treatment with the Optune is not expected to cause any serious side effects. However, it is possible that treatment may cause any of the following:

- Local warmth and tingling "electric" sensation beneath the transducer array
- Allergic reaction to the adhesive or the gel
- Skin irritation or skin breakdown
- Infection at the sites of electrode contact with the skin
- Transducer array overheating leading to pain and/or local skin burns
- Headache
- Fatigue

6.2 Pembrolizumab Administration

Pembrolizumab 200 mg will be given intravenously every 3 weeks (+/- 4 days) beginning no sooner than 3 weeks after the start of Optune. Pembrolizumab will be given intravenously over the course of approximately 30 minutes on an outpatient basis. For subjects who receive pembrolizumab alone after the completion of TMZ or due to TMZ intolerance, pembrolizumab infusions may be administered per the treatment plan if absolute neutrophil count (ANC) is $\geq 1.0 \times 10^9$ /L, and the platelet count is $\geq 50 \times 10^9$ /L, and if it is determined by the treating physician that the cytopenia was unlikely to be related to pembrolizumab treatment.

6.2.1 Premedication Administration of Pembrolizumab

No premeditations are required, but antiemetics may be given as per institutional practice if needed.

6.3 Temozolomide Administration

Patients will begin treatment with adjuvant TMZ at least 4 weeks but no more than 6 weeks from last dose of concomitant temozolomide or radiation therapy (the latter of the two). A minimum of 6 and maximum of 12 cycles of adjuvant TMZ will be given depending on tolerability and toxicity.

6.3.1 Adjuvant Temozolomide Treatment

- Adjuvant Phase Cycle 1 (4-6 weeks after chemoradiation): Dosage in Cycle 1 will be 150 mg/m² PO daily for 5 consecutive days per 28 (+7) day cycle.
- Cycle 2 (up to Cycle 12): At the start of Cycle 2, the dose of TMZ will be increased to 200 mg/m² PO daily for 5 consecutive days per 28 (+7) day cycle, if the CTC nonhematologic toxicity for Cycle one is Grade ≤ 2 (except for alopecia, nausea and vomiting), absolute neutrophil count (ANC) is ≥ 1.5 x 10⁹/L, and the platelet count is ≥ 100 x 10⁹/L. The TMZ dose will remain at 200 mg/m² PO daily for 5 consecutive days per 28 (+7) day cycle for each subsequent cycle except if toxicity occurs (see section 8.1). If the dose is not increased at Cycle 2 due to toxicity, escalation should not occur in subsequent cycles; however, it is appropriate to decrease to cycle 1 dose in cycles 2-12 if toxicity occurs.

6.4 Follow-Up Evaluations During The 12 Cycles of Adjuvant TMZ

All patients will be seen before Cycle 1 of TMZ, before starting the pembrolizumab, and every 3 weeks (+/-4 days) before each subsequent pembrolizumab dose at an outpatient clinic until they complete all 12 cycles of adjuvant TMZ or discontinue TMZ due to toxicity or first progression. Optune compliance reports will be collected remotely or in the clinic setting approximately every 4 (+/- 1) weeks. Contiguous data will be sufficient for Optune compliance reporting, per SOC for the Optune Device.

At each visit the following will be performed except otherwise specified:

- Physical exam and performance status (KPS)
- Blood exams
 - o CBC with differential within 3 days prior to starting each cycle of temozolomide
 - Complete Metabolic Panel prior to each cycle of pembrolizumab and prior to starting each cycle of temozolomide (+/- 7 days)
 - o PT/PTT, INR for patients receiving relevant anti-coagulants
 - o TSH, Free T4 prior to the first infusion of pembrolizumab and then prior to every other pembrolizumab infusion thereafter
- Study lab as specified
- Steroid dose
- Concomitant Medications
- Record of Adverse Events
- TTF compliance report (only every 4 +/- 1 weeks)

An MRI will be performed every 2 months (+/- 7 days) following the baseline MRI until second progression (when study treatment will be terminated). In the case of clinical progression an unscheduled MRI will be obtained within 1 week of the investigator becoming aware of the clinical progression. Contrast agent type and dose will be kept constant for each patient between scans. Disease will be assessed as per iRANO criteria [64] [65] with allowance for potential immune mediated effects at first appearance. No additional MRIs will be required by the study after second progression. Medical follow-up will continue for 30 (+/- 7) days after treatment termination in

order to capture treatment related toxicities. After this visit, mortality will be assessed based on telephone interviews with the patients or the patients' caregivers every 3 months.

6.5 Evaluation After Adjuvant TMZ Until Treatment Termination

After 12 cycles of adjuvant TMZ, patients will be seen and examined before every three pembrolizumab doses. Pembrolizumab and Optune can continue up to 2 years. Optune compliance reports will be collected remotely or in the clinic setting every 4 (+/- 1) weeks. Brain MRI and quality of life assessment will be performed every 2 months (+/- 7 days) until study termination or second progression, whichever comes first. In case of clinical progression an MRI will be performed within a week of the treating physician being made aware. Contrast agent type and dose will be kept constant for each patient between scans. Disease will be assessed as per iRANO criteria [64] [65] with allowance for potential immune mediated effects at first appearance.

At each visit the following will be performed except for otherwise noted:

- Physical exam and performance status (KPS)
- Blood exams
 - o CBC with differential within 3 days prior to starting each cycle of temozolomide
 - Complete Metabolic Panel prior to each dose of pembrolizumab and prior to starting each cycle of temozolomide (+/- 7 days)
 - o PT/PTT, INR for patients receiving relevant anti-coagulants
 - o TSH, Free T4 prior to the first infusion of pembrolizumab and then prior to every other pembrolizumab infusion thereafter
- Study lab as specified
- Steroid dose
- Concomitant Medications
- Record of Adverse Events
- TTF compliance report (every 4 +/-1 weeks)

6.6 Post Treatment Evaluations

Treatment will continue according to the protocol until toxicity, second progression or 24 months (the earlier of the three). After treatment termination the patient will be followed every three months via phone call or collected from clinic notes for survival follow up until death or for 5 years, whichever occurs first.

Subjects will be evaluable for survival analysis if they have received Optune treatment, AND have received at least one dose of pembrolizumab, AND have received adjuvant temozolomide. Subjects that are not evaluable for survival analysis will be replaced.

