10.1 Primary Endpoint

Our primary endpoint is progression-free survival time from enrollment to progression or death or censoring, whichever occurs first, with the goal of determining whether the triple combination treatment increases PFS in newly diagnosed GBM patients when compared to TTFields+TMZ historical control patients from the EF-14 study. We will use one-sample log-rank test to compare PFS between the triple combination arm relative to the historical control arm.

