10.2 Secondary endpoints

We are proposing 3 secondary endpoints:

- 1. Toxicity and tolerability of the triple combination treatment in newly diagnosed GBM patients.
- 2. Overall survival time from enrollment to death or censoring, whichever occurs first() and radiographic response (RR) at 6, 12, 18 and 24 months of the triple combination in newly

diagnosed GBM, as compared to the historical control arm.

3. Augmentation of TTFields-initiated glioma-specific immune reaction by pembrolizumab.

We will estimate proportions and 95% confidence intervals for patients in the triple combination arm who experience toxicities and other types of AEs and SAEs. We will use the log-rank test to compare OS between the triple combination arm relative to the historical control arm. We will use one-sample proportion test to compare RR between the triple combination arm and historical control arm. We will use mixed effect regression to assess changes in response variables related to glioma-specific immune reaction before, during, and after treatment with pembrolizumab.

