10.3 Sample Size Considerations

To determine if the proposed sample size of 24 patients enrolled in the triple combination arm will allow us to detect a clinically relevant improvement in median PFS relative to the median PFS of 6.7 months observed in the historical control arm, we assumed an accrual period of 12 months, an accrual rate of 2 patients per month, an additional 18 months of follow-up after the end of accrual, and proportional hazards. After confirming that the Weibull distribution could reasonably be used to characterize PFS times in the historical control arm, we estimated the Weibull shape parameter k from the historical control PFS curve. The shape parameter k determines if the hazard rate underlying a survival curve is accelerating over time (k>1), constant over time (k=1; identical to exponential survival), or decelerating over time (k<1). Based on a shape parameter estimate of k=0.88 with empirical 95% confidence interval (0.82,0.95) obtained via simulation of the historical control data, our proposed sample size of 24 patients in the triple combination arm should allow us to detect in improvement in PFS of 6 to 8 months with 80% power and a 1-sided significance level of 0.05 (detectable effect size methodology from Wu and Xiong, 2014 [69]).

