11. STUDY CALENDAR

	Screening	Week 0 (TMZ/ Optune Cycle 1)	Week 4 (TMZ/ Optune Cycle 2, Pembro Dose 1)	Week 7 (Pembro Dose 2)	Week 8 & every 4 weeks on-treatment management (TMZ Cycles 3-12)	Week 10 & every 3 weeks on-treatment management (Pembro Dose 3 and beyond)	Post TMZ Treatment follow-up	Post- Pembro Treatment follow-up	Post treatment termination
Informed Consent	X^1								
Medical History	X^{12}								
Pregnancy Test	X^{17}								
PBMC & Urine	X^{18}			X^{18}				X^{19}	
Specimen									
Physical Exam, KPS	X^8		X^8	X^8		X^8	X^8	X^8	
Tumor Tissue	X^{21}							X^{22}	
PT/PTT, INR		X^{23}	X^{23}		X^{23}		X^{23}		
CBC with Differential	X	X^9	X^9		X ⁹		X^{15}	X	
CMP	X	X^{10}	X^{10}	X^{10}	X^{10}	X^{10}	X^{15}	X	
TSH/Free T4	X		X^{11}	X^{11}		X ¹¹	X^{15}	X	
MRI	X^2				X^{13}		$X^{13, 20}$		
Temozolomide Cycle		X^3	X^4		X^4				
Pembrolizumab			X ⁵	X^5		X^5	X^5		
Optune		X^6	X^6		X^6				
Optune Compliance			X^6					X	
AE Assessment	X^7	X^{16}	X^{16}		X^{16}			X	
Concomitant	X	X	X	X	X	X		X	
Medications									
Survival Contact									X^{14}

- 1. No study-specific procedures are to be performed prior to obtaining informed consent. However, assessments performed according to SOC prior to consent may be used to fulfill the screening requirement. Study treatment should start no later than 6 weeks from last dose of concomitant Temozolomide or radiation therapy (the latter of the two).
- 2. Patients will undergo SOC brain MRI scans with RANO disease/response evaluation at screening, 4 weeks (+7/-14 days) after end of chemoradiation.
- 3. Patients will begin treatment with temozolomide at 4 weeks (+14 days) from end of radiotherapy, week 0. Cycle 1 will be dosed at 150mg/m² daily for 5 consecutive days of a 28-day cycle.
- 4. Patients will begin treatment with temozolomide Cycle 2 and subsequent cycles every 4 weeks (+7 days) at 200mg/m² PO daily for 5 consecutive days, unless toxicity occurs. See 6.3.1 for dose escalation parameters.
- 5. Pembrolizumab will be given every 3 weeks (+/- 4 days) beginning no sooner than 3 weeks from the start of Optune. For subjects who receive pembrolizumab alone after the completion of TMZ or due to TMZ intolerance, pembrolizumab infusions may be administered per the treatment plan if absolute neutrophil count (ANC) is $\geq 1.0 \times 10^9$ /L, and the platelet count is $\geq 50 \times 10^9$ /L, and if it is determined by the treating physician that the cytopenia was unlikely to be related to pembrolizumab treatment.

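### Survival analysis is limited to pembrolizumab-treated patients and the others are replaced, but PFS and OS run from enrollment, so the test counts expected events over weeks in which some observed events are dropped

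*Combined protocol and SAP*

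**What the plan says.** Section 6.6 sets the analysis set: "Subjects will be evaluable for survival analysis if they have received Optune treatment, AND have received at least one dose of pembrolizumab", together with adjuvant temozolomide. It continues: "Subjects that are not evaluable for survival analysis will be replaced".

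Section 10.1 sets the clock: "Our primary endpoint is progression-free survival time from enrollment to progression or death or censoring, whichever occurs first". It also sets the test: "We will use one-sample log-rank test to compare PFS between the triple combination arm relative to the historical control arm". For OS, Section 10.2 gives: "Overall survival time from enrollment to death or censoring, whichever occurs first".

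Section 6.2 has pembrolizumab "beginning no sooner than 3 weeks after the start of Optune", and the Section 11 calendar places dose 1 at Week 4. No latest date for dose 1 is given. Section 6 stops protocol pembrolizumab at first progression but then allows it again at the treating physician's discretion.

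Sections 6.1 and 13 add a second rule. A patient still below 50% Optune compliance in the third 4-week period is removed, is not evaluable for survival analysis and is replaced, but stays evaluable for toxicity. Section 10 contains no landmark, no delayed entry and no all-enrolled analysis.

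**The concern.** A patient qualifies for the analysis only by reaching an event that occurs 3 to 4 weeks or more after the clock starts. A death in that interval always removes the patient. A progression in that interval removes the patient unless pembrolizumab is given anyway, so in an open-label trial a decision taken after the outcome can determine whether the outcome counts.

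The one-sample log-rank test compares observed events O with the events E expected from the control hazard over each patient's follow-up. Here E accumulates from enrollment, while some of the matching early events cannot appear in O. With no pembrolizumab effect the filter can therefore only push the result toward benefit. With 24 patients, one or two dropped events are visible in the error rate.

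**Working it through.** **Inputs (Section 10.3).** n = 24; control median PFS 6.7 months; Weibull shape k = 0.88 (0.82 to 0.95); 12 months of accrual plus 18 of follow-up; one-sided 0.05. First dose at L = 4 weeks (calendar) or 3 weeks (Section 6.2 minimum).

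**Assumptions that the plan does not state.** Enrollment equals Week 0. The reference hazard is the plan's Weibull. The share p of pre-dose events that leads to replacement is unknown and is varied. The variance form is not given, so both usual forms are shown.

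**1. The plan's own figure.** With H0(t) = ln 2 × (t/6.7)^k, uniform accrual and proportional hazards, the detectable gain in median PFS at 80% power is 7.6, 6.7 and 5.9 months for k = 0.82, 0.88 and 0.95. The stated 6 to 8 months is reproduced.

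**2. Expected events before dose 1.** 4 weeks is 0.92 months. H0(L) = 0.693 × (0.92/6.7)^0.88 = 0.121, so F0(L) = 1 − exp(−0.121) = 0.114, or 24 × 0.114 = 2.7 modeled events. If every one were replaced, E would carry 24 × 0.121 = 2.9 events with no possible match in O; simulation gives O = 20.7 and E = 23.6.

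**3. Type I error.** Each event before L is replaced with probability p by a new patient under the same rule. Reject if (O − E)/√V < −1.645. There were 400,000 simulated trials per scenario (standard error at most 0.0006); repeat runs agree within about 0.002. Mean replaced patients = 24 × pF0/(1 − pF0). The null median solves S0(t) = 0.5 × (1 − pF0).

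| p | mean replaced | V = E | V = (O+E)/2 | apparent median, no drug effect |
|---|---|---|---|---|
| 0 | 0 | 0.038 | 0.051 | 6.7 |
| 10% | 0.28 | 0.042 | 0.057 | 6.8 |
| 25% | 0.70 | 0.049 | 0.065 | 7.0 |
| 50% | 1.45 | 0.065 | 0.084 | 7.3 |
| 100% | 3.08 | 0.108 | 0.139 | – |

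**4. Sensitivity.** For k = 0.95 to 0.82, p = 10% gives 0.042–0.043 / 0.056–0.058 and p = 25% gives 0.047–0.052 / 0.062–0.069. With a 3-week interval, p = 10% gives 0.041/0.055 and p = 25% gives 0.047/0.062. A gap between enrollment and Week 0 raises every figure: an assumed 2-week gap (L = 6 weeks) lifts the full-replacement value under V = E from 0.108 to 0.161.

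**5. How many pre-dose events are plausible.** Treatment starts 4 to 6 weeks after chemoradiation (Section 4.1), so a Week 4 dose falls at 8 to 10 weeks. Baseline MRI is at 2 to 5 weeks (Section 6: 4 weeks, +7/−14 days) and the next is 2 months ± 7 days later (Section 6.4), at roughly 10 to 15 weeks. Scheduled scans therefore rarely precede dose 1. Before 12 weeks, Section 13.1 accepts only enhancement outside the radiation field or histologic proof, and Section 4.2 excludes progressive disease at entry. This points to the low rows of the table.

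**6. Delayed entry.** With E_i = H0(X_i) − H0(L_i), type I error returns to 0.038/0.051. At HR 0.55 (median 6.7 × (1/0.55)^(1/0.88) = 13.2 months, a gain of 6.5) power is 0.80/0.83 against 0.81/0.84 with no filter. If patients who progress before dose 1 use up places among the 24 and are not replaced, power falls to about 0.77/0.81 in the model's worst case.

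**The case against.** Four points can fairly be made for the plan.

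- **Section 6.6 does not name PFS.** Its sentence follows one on survival follow-up until death, so it could mean OS only. That stands as an ambiguity. The PFS reading is an inference: Sections 6.1 and 13 contrast survival analysis with toxicity endpoints, and no other PFS set is given. If OS alone is meant, the PFS figures above fall away, but OS also starts at enrollment and has the same misalignment.
- **Few events can occur before dose 1.** This stands and governs the size. It does not align the clock with the entry condition.
- **The early Weibull hazard drives the numbers.** With k below 1 the hazard is highest near time zero, and Section 10.1 does not say that the Weibull is the test's reference. The 11.4% by 4 weeks is a model tail, not an observed rate.
- **A treated-patient set suits a question about the triple combination.** Agreed. The defect is the mismatch between that set and time zero.

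A reader might infer that the primary test runs at 11% to 14% instead of 5%. The documents do not support that: it needs every modeled early event to occur and to be replaced, whereas Section 6 allows dosing after progression and Section 13.1 makes early progression hard to declare. Nor should one infer that the sample size statement is wrong, since it reproduces.

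**Conclusion.** The misalignment is in the text, and with no drug effect its direction is fixed in favor of the triple combination. The probable inflation is small: about 0.004 to 0.006 at 10% replacement and 0.011 to 0.014 at 25%, across the two variance forms. Under variance E and k = 0.88 the total stays at or below 0.05 up to 25%. Under (O+E)/2 the unfiltered test is already at 0.051, so exceeding 0.05 there is not due to the filter alone. The 50% and 100% rows are upper-range figures only.

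The sizes rest on reading survival analysis as including PFS, on enrollment at Week 0, on the plan's Weibull as the reference hazard and on an assumed replacement share. The point should be fixed because the remedy is cheap and the plan leaves that share open. Confidence is medium: firm on the mechanism, less so on the size. The direction of the compliance rule's effect is unknown.

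**What to change.** **Sections 6.6 and 10.1**

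- Say whether survival analysis covers PFS, OS or both, and state the variance form and the reference hazard.
- If the treated set stays primary, use delayed entry at first pembrolizumab dose: E_i = H0(X_i) − H0(L_i), with L_i the time from enrollment to first dose. Admit patients who are alive and progression-free at first dose for PFS, and alive for OS.
- State that patients who progress before first dose are replaced for PFS whether or not they are later dosed. If they are not to be replaced, state the lower power.

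**Sensitivity analysis.** Analyze from enrollment all patients who start adjuvant temozolomide or Optune, with nobody dropped for a missing pembrolizumab dose or low Optune compliance. The plan schedules only survival contact after treatment ends, so use progression data from routine care where available. Otherwise censor PFS at the last assessment and note that this censoring may be informative. OS needs no new data.

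**Reporting.** Give the numbers undosed, removed and replaced, with reasons, and show low-compliance removals separately.

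**Cost.** Wording changes and about 1 point of power if pre-dose progressors are replaced (up to about 3 to 4 points in the model's worst case if not). Replacement may add a few enrolled patients: 3.1 on average in the model's upper bound with no drug effect. No new study assessments are needed.

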7. CORRELATIVE STUDIES

7.1 Blood Specimens

7.1.1 Collection of Specimens

Sixty milliliters of blood will be collected into 6 green top tubes (with heparin) for isolation of PBMCs at the following time points:

- No more than two weeks prior to starting adjuvant therapy.
- No more than one week prior to the first dose of pembrolizumab.
- No more than one week prior to the second dose of pembrolizumab and then approximately 2-, 4-, 6-, 12-, and 24-months after the first dose of pembrolizumab.
- At the end-of-treatment with Pembrolizumab the research blood draw will be obtained at the next scheduled clinic visit. Clinic visits after treatment concludes shall be scheduled per standard care.
 - o If study treatment is ended due to disease progression or toxicity prior to the 24 months study term, a final research blood draw will be obtained within 30 (+/- 7) days of progression and no further research blood draws will be performed (unless the patient continues on Optune therapy to second progression as detailed in section 6).
 - o If the study treatment is ended at 24 months as stipulated by the protocol, the endof-treatment sample will be obtained at the next SOC visit and at the time of progression.
- In the event of surgical resection or biopsy (refer to section 7.2.1), research labs will be collected as close to the date of surgery as possible, but not more than two weeks prior to surgery.

